APPENDIX B STRONG INDUCERS OF CYP ISOENZYMES

CYP Enzymes	Medications
CYP3A4/3A5	avasimibe, carbamazepine, phenytoin, rifampin, St. John's wort, mitotane, enzalutamide
CYP2B6	Carbamazepine
CYP2C19	rifampin and ritonavir
CYP2C9	Currently no known inducers

Please note the following: This is not an exhaustive list. For an updated list, refer to the following link:
<http://www.fda.gov/Drugs/DevelopmentApprovalProcess/DevelopmentResources/DrugInteractionsLabeling/ucm080499.htm>.

## 2 INTRODUCTION

This statistical analysis plan (SAP) was prepared in accordance with Protocol GBT440-026, dated 5June2017 (Amendment 2), and was generated prior to locking the study database. This SAP specifies the safety analyses to be performed for an abbreviated report. Planned pharmacokinetic (PK) analyses will be described in a separate analysis plan.

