3.2 Endpoints

3.2.1 Primary Endpoint

The primary endpoint is change and % change from baseline in oxygen saturation at rest (SpO₂ or SaO₂), measured while breathing room air, at Days 30 and 90.

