5.5.3 Arterial Blood Gases (ABG)

Arterial blood samples will be taken at each scheduled OTT: Day 1 (baseline), Days 30, 90, and 120. Two samples will be drawn at each test:

- Prior to the beginning of the test (i.e., prior to beginning to walk) while resting and breathing room air (i.e., with no oxygen being delivered to the subject) and
- Immediately after completion of the OTT while receiving oxygen at the flow rate being delivered at the end of the test

An Allen's test should be performed prior to the resting ABG at each OTT.

The necessary equipment for performing the ABG should be prepared prior to beginning the OTT and readily available for both samples. Likewise, the necessary materials and equipment to transport the ABG samples for analysis should be readily available to ensure the integrity of the samples is not compromised.

5.5.4 6-Minute Walk Test (6MWT)

Functional exercise capacity will be evaluated at Day 1 (baseline) and Days 30, 90, and 120 using the 6MWT.

Refer to the 6MWT manual for complete instructions.

Guidelines developed by the ERS/ATS will be used for conducting the test and interpreting the results ([ATS 2002](#) and [Holland 2014](#)). Instructions for the conduct of the 6MWT will be provided in a separate manual.

The 6MWT should be performed at each scheduled visit at approximately the same time of day (e.g., in the morning) and after spirometry and DL_{CO} assessments (if scheduled on the same visit day).

As part of the 6MWT, SpO₂, heart rate, and the Borg Dyspnea Scale will be measured at the following time points: prior to starting the test, during the test, at completion of the test, and 1 minute and 2 minutes after test completion.

Refer to the 6MWT manual for complete instructions.

For safety reasons, all subjects should be clinically stable, as determined by the study Investigator or the performing technician, prior to performing the 6MWT.

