11 DATA ANALYSIS AND STATISTICAL PLANS

This section describes the statistical methodology to be used in the analysis of the protocol endpoints. Details of all planned analyses will be specified in a separate Statistical Analysis Plan (SAP).

Data will be summarized using descriptive statistics. Continuous variables will be summarized using mean, standard deviation (SD), coefficient of variation (CV%, as appropriate), median, minimum, maximum, and, as appropriate, geometric mean. Categorical variables will be summarized by presenting the number (frequency) and percentage in each category.

Data will be summarized by dose level (900 mg, 1500 mg) and overall (total subjects). All collected data will be presented in data listings.

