11.3 Statistical Analyses

11.3.1 Efficacy Analyses

The analysis of the primary and secondary endpoints will be summarized descriptively. Each endpoint will be summarized by dose group and overall (total subjects).

Full details of the analysis methods, including how missing data will be handled, will be provided in the SAP.

11.3.2 *Safety Analyses*

Safety and tolerability will be assessed by incidence, severity and changes from baseline of all relevant parameters including AEs, laboratory evaluations, vital signs, and ECGs.

AEs will be coded using the Medical Dictionary for Regulatory Activities (MedDRA). The number and percentage of subjects experiencing 1 or more AEs will be summarized by dose group and overall, relationship to study drug and severity according to system organ class and preferred term. Additional summaries will be provided for SAEs and events resulting in permanent discontinuation of study drug.

Laboratory parameters will be summarized using descriptive statistics and by post-dose shifts relative to baseline. Laboratory values outside normal limits will be identified in the subject listings and will include flags for high and low values.

Vital sign results and ECGs will also be summarized descriptively for each scheduled protocol time point.

11.3.3 *PK and PK/PD Analyses*

A listing of PK sample collection times as well as derived sampling time deviations will be provided. A subject listing of all concentration-time data for each treatment, and study day will be presented. PK variables will be summarized using appropriate descriptive statistics (e.g., n, mean, SD, CV%, minimum, median, and maximum, and/or geometric mean) by part, dose, and study day.

Graphical presentations of key PK parameters and concentrations will be used as appropriate. Figures of individual concentrations versus time will be presented by subject.

PK/PD analyses will be performed.

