### 2.2 Primary Objective

To evaluate the effect of GBT440 on oxygen saturation at rest, breathing room air, on Days 30 and 90 compared to baseline.

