## **3 STUDY ENDPOINTS**

Endpoints described below are for the safety summaries only.

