#### ***8.4.5 Vital Signs and Physical Examination***

Actual value and change from baseline for vital sign and pulse oximetry results including blood pressure (SBP[mmHg], DBP[mmHg]), heart rate (bpm), respiratory rate (bpm), temperature (C), SpO2(%) and flow rate (L/min) will be summarized at each scheduled visit.

Physical examination results including height, weight, and BMI will be summarized by the absolute value and change from baseline at each scheduled visit during the study. Height will presented for Screening only. Baseline is the Screening visit.

Baseline for vital signs is defined as the average of Screening and Day 1 measurements taken before the first dose of GBT440.

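### SAP 8.1 reverses the sign of change from baseline, and the SAP's declared safety-only scope leaves the room-air saturation objective with no stated place of analysis

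*SAP*

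**What the plan says.** **Change from baseline.** SAP 8.1 tells the programmer to take the post-baseline value away from the baseline value. The percent-change formula that follows runs the other way: post-baseline minus baseline, divided by baseline. Change from baseline is then requested in SAP 8.4.4 (chemistry, liver function, hematology, erythropoietin), 8.4.5 (vital signs, SpO2, flow rate, weight, BMI) and 8.4.6 (ECG intervals). None of these sections asks for percent change. SAP 8.4.6 also counts subjects whose QTcF increases by more than 30 and more than 60 ms.

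**Scope.** SAP 2 states: "This SAP specifies the safety analyses to be performed for an abbreviated report". SAP 3 adds: "Endpoints described below are for the safety summaries only". SAP 6 defines only the Safety Population. SAP 2.2 nevertheless restates the primary objective: "To evaluate the effect of GBT440 on oxygen saturation at rest, breathing room air, on Days 30 and 90 compared to baseline". PK is sent to a separate plan (SAP 2 and 8.5); no other plan is named for efficacy.

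Protocol 11 defers the details of all planned analyses to the SAP. Protocol 11.3.1 commits to descriptive summaries of the primary and secondary endpoints by dose group and overall, and says: "Full details of the analysis methods, including how missing data will be handled, will be provided in the SAP".

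**Listings.** Protocol 11 promises listings of all collected data. SAP 8.1 promises them only for eCRF data that appear in a summary table.

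**The concern.** A definition in the general-methods section governs every table that uses the term. Protocol 1.5.4 names increased resting heart rate and erythropoietin among the signals for subclinical tissue hypoxia. With the sign reversed, a rise in either is printed as a negative mean change, which looks like a fall. In the ECG output, the mean QTcF change could be negative while the same data yield counts of subjects with an increase.

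On scope, the report as specified contains no result for the study's primary objective and does not say where one will be found. It does contain something that resembles one. SAP 8.4.5 says: "SpO2(%) and flow rate (L/min) will be summarized at each scheduled visit". Those rows share names with the primary endpoint and the first secondary endpoint but are measured under different conditions.

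**Working it through.** There is no power or sample-size figure to reproduce; SAP 4 says the size is not based on power.

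**Step 1: sign.** The values below are assumptions for illustration, not trial data. The rule as written is baseline − post; the usual definition is post − baseline; the SAP's percent formula is (post − baseline)/baseline × 100.

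| Baseline → post | Rule as written | Post − baseline | SAP percent formula |
|---|---|---|---|
| QTcF 440 → 475 ms | 440 − 475 = −35 | +35 | 35/440 = +7.95% |
| QTcF 440 → 505 ms | 440 − 505 = −65 | +65 | 65/440 = +14.77% |
| QTcF 475 → 440 ms | 475 − 440 = +35 | −35 | −35/475 = −7.37% |
| Heart rate 80 → 90 bpm | 80 − 90 = −10 | +10 | 10/80 = +12.5% |
| Hemoglobin 140 → 155 g/L | 140 − 155 = −15 | +15 | 15/140 = +10.71% |

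The rule and the percent formula disagree in sign in every row; the absolute size is the same. Because no planned table uses percent change, only the reversed rule reaches the output.

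**Step 2: QTcF categories.** If the >30 ms flag were derived from the variable as written, the 35 ms rise (−35) would not be flagged and the 35 ms fall (+35) would be. If it is derived from the word increase in SAP 8.4.6, the counts are right.

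**Step 3: efficacy coverage.** Protocol 3.2.1 has 1 primary endpoint bullet, 3.2.2 has 7 secondary and 3.2.3 has 3 exploratory. Matched against SAP 3 and 8, the number with an analysis is 0 of 1, 0 of 7 and 0 of 3.

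**Step 4: data that exist for the primary objective.** Protocol 5.5.3 says: "Arterial blood samples will be taken at each scheduled OTT: Day 1 (baseline), Days 30, 90, and 120". One of the two samples at each test is taken at rest on room air. For Days 1, 30 and 90 that is at most about 32 × 3 = 96 samples. They enter no SAP table, so the SAP 8.1 listing rule does not reach them, although the Protocol 11 listing rule does. The two rules conflict.

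**Step 5: the SpO2 and flow rows in SAP 8.4.5.** The primary endpoint is "oxygen saturation at rest (SpO₂ or SaO₂), measured while breathing room air". Protocol 5.5.2 has vital-sign SpO2 taken on supplemental oxygen at the subject's usual flow. The secondary endpoint is the flow needed to hold 89 to 92%, and the oxygen titration test (OTT, Protocol 5.5.1) uses the lowest flow that does so. The flow recorded with vital signs is the usual one. Neither row is the endpoint it resembles.

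**The case against.** The sign sentence is very probably a wording slip. The percent formula beside it has the usual direction, SAP 8.4.6 speaks of an increase, and actual values are tabulated next to the changes, so a careful reader could recover the direction. All of that stands and limits the harm. It does not make the sentence right: it is the only definition of change in the SAP, and a programmer who follows it produces reversed tables.

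On efficacy, the SAP declares its scope in two places. The protocol already supplies a minimal plan: descriptive statistics, by dose and overall, in the Efficacy Evaluable Population, with no hypothesis test. That also stands, and no inferential analysis is lost. What remains is narrower: no reason for leaving efficacy out, no pointer to where it will be reported, and objectives restated as if they would be addressed.

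A reader might infer more than the documents support:
- **That efficacy was concealed.** The narrowing is stated openly, and nothing in the text shows a motive.
- **That the arterial data will go unlisted.** Protocol 11 promises listings of everything collected; the fault is the conflict with SAP 8.1.
- **That the QTcF counts are wrong.** They are worded as increases and fail only if built from the SAP 8.1 variable.
- **That room-air eligibility readings contaminate the vital-sign SpO2 baseline.** Protocol 5.5.2 and the opening of Table 15-2 footnote i both place that reading on supplemental oxygen.
- **That arterial SaO2 must be the primary measure.** The protocol allows SpO2 or SaO2, and the OTT manual, which was not supplied, may set a room-air SpO2 reading.

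**Conclusion.** Both parts hold, at different strengths.

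The change definition is wrong as written. Followed literally, it reverses the sign of every mean change in SAP 8.4.4 to 8.4.6, erythropoietin and heart rate included. This assumes literal programming.

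The efficacy gap is a declared narrowing that leaves the protocol's deferral to the SAP unmet: 0 of 1 primary and 0 of 7 secondary endpoint bullets have an analysis in the SAP, and it does not say whether or where one will be reported. The figure of 96 samples is a ceiling that assumes full enrolment and complete attendance. That readers would take the on-oxygen SpO2 rows for the primary endpoint is a risk, not a certainty, but a label removes it.

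**What to change.** 1. In SAP 8.1, define change from baseline as the post-baseline value minus the baseline value. Cost: one sentence.
2. Choose one of two courses for efficacy.
   - Add by-visit descriptive tables, by dose and overall, of resting room-air saturation at Days 1, 30 and 90 and of the OTT flow rate. Show both SaO2 and SpO2 where both exist, use observed values with n at each visit, and list the arterial blood gas data. The data are already collected.
   - Or state that efficacy is not analysed in this report and where it will be reported. Cost: a few sentences.
3. Label the SpO2 and flow-rate rows of SAP 8.4.5 as taken on usual supplemental oxygen.
4. Bring the listing rule in SAP 8.1 into line with Protocol 11, or state the departure.

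The downside is a slightly longer report. The study is open label, so any choice of a primary saturation measure made now should be declared as made after data were available; showing both measures avoids having to choose.

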### 2.1 Overview of Study Design

This is an open label study that will be conducted in two parts. Together, Parts A and B will provide safety and efficacy data across the two GBT440 doses that are expected to improve oxygen saturation in the enrolled subjects.

Approximately up to 32 eligible subjects will be enrolled in the study.

- In Part A, up to approximately 16 eligible IPF subjects will receive 900 mg of GBT440 administered orally as  $3 \times 300$  mg capsules or tablets once daily for 90 days.
- In Part B, up to approximately 16 eligible IPF subjects will receive 1500 mg of GBT440 administered orally as  $5 \times 300$  mg capsules or tablets once daily for 90 days.

The screening period for each subject commences when the subject undergoes the first study-specific screening assessment and must be completed and tests evaluated before dosing (Day 1). Subjects may be rescreened up to 2 times, if deemed appropriate by the Principal Investigator. The rescreening visit should not occur sooner than 10 calendar days after the failed screening visit.

After the screening visit, the study includes the following study periods:

- Treatment period (90 days): Subjects in Part A will receive 900 mg ( $3 \times 300$  mg) and subjects in Part B will receive 1500 mg ( $5 \times 300$  mg) capsules or tablets daily
- Safety follow up (30 days): Safety will be assessed for at least 5 half-lives after the last dose of GBT440 in both Parts A and B

### 2.2 Primary Objective

To evaluate the effect of GBT440 on oxygen saturation at rest, breathing room air, on Days 30 and 90 compared to baseline.

### 2.3 Secondary Objectives

- To evaluate the effect of GBT440 on the requirement for supplemental O2 at rest and post-exercise at Days 30 and 90 compared to baseline

- To evaluate the effect of GBT440 on resting and post-exercise Alveolar-arterial O2 tension difference [P(A-a)O2] at Days 30 and 90 compared to baseline
- To evaluate the effect of GBT440 on six-minute walk distance (6MWD) at Days 30 and 90 compared to baseline
- To evaluate the effect of GBT440 on IPF-related symptoms, using patient reported outcomes (PROs), at Days 30 and 90 compared to baseline
- To evaluate pulmonary function at Day 90 compared to baseline
- To evaluate the safety and tolerability of 900 mg and 1500 mg GBT440 dosed daily for 90 days
- To evaluate the PK of GBT440

## **2.4 Exploratory Objectives**

- To evaluate the effect of GBT440 on the need for any O2 while at rest at Days 30 and 90 compared to baseline
- To compare the change in O2 requirement between the two O2 flow rate allocation groups
- To evaluate the effect of GBT440 on extent of activity during daily living at Days 30 and 90 compared to baseline

## **3 STUDY ENDPOINTS**

Endpoints described below are for the safety summaries only.

### **3.1 Safety Endpoints**

The safety outcome measures for this study are the frequency and severity of treatment-emergent adverse events and tolerability of GBT440 administered daily orally for 90 days.

## **4 DETERMINATION OF SAMPLE SIZE**

Sample size is not based on statistical power. The study will enroll up to approximately 32 subjects; up to approximately 16 subjects in Part A and up to approximately 16 subjects in Part B.

## **5 METHOD OF STUDY DRUG ASSIGNMENT**

All subjects who are dosed will receive either 900 mg or 1500 mg of GBT440 administered orally daily for up to 90 days.

## **6 ANALYSIS POPULATION**

**Safety Population:** All subjects who receive any amount of study drug will be included in the Safety population. The Safety population will be the primary population for all safety data presented.

## 7 ANALYTIC DEFINITIONS

Definitions of terms used for the calculation of derived variables and general terms used for the analyses are provided in this section.

### 7.1 Study Day

Study Day 1 corresponds to the date of the first dose of any study drug.

Unless otherwise specified, the timing of all study-related events, assessments, and interventions will be calculated relative to Study Day 1. For events, assessments, and interventions after Study Day 1, study day represents the elapsed number of days from Study Day 1, inclusive:

$$\text{Study Day } n = (\text{Date of assessment} - \text{Date of Study Day 1}) + 1 \text{ day}$$

Study Day -1 will be the day before Study Day 1, and in general for assessments prior to Study Day 1, study day is defined as:

$$\text{Study Day } n = (\text{Date of assessment} - \text{Date of Study Day 1})$$

For listings (such as for adverse events) that include the derivation of “days since last dose,” this is defined as event date – date of last dose. Events that occur on the same day as the last dose of study drug will therefore be described as occurring zero days from the last dose of study drug.

### 7.2 Baseline

Unless otherwise specified, the baseline value for a given variable is defined as the last measurement for the variable prior to the first dose of GBT 440. For variables where multiple assessments prior to first dose are collected, the average of those assessments is calculated for the baseline value (eg, vital signs).

## 8 STATISTICAL METHODS

### 8.1 General Considerations

Data will be summarized using descriptive statistics. Continuous variables will be summarized using mean, standard deviation (SD), median, minimum, and maximum. Categorical variables will be summarized by presenting the number (frequency) and percentage in each category. Minimum and maximum will be presented to the same decimal places as the collected data; means and medians will be presented to one additional decimal place than reported in the collected data. Standard deviations will be presented to two additional decimal places than reported in the collected data.

Change from baseline to post-baseline values will be calculated by subtracting the post-baseline value from the baseline value. The percentage change from baseline values to post-baseline values will be calculated using the following formula:

$$([post\text{-}baseline\ value - baseline\ value] / baseline\ value) \times 100\%$$

Data will be summarized by dose level (900 mg, 1500 mg) and all GBT440.

Individual subject data recorded on the electronic case report forms (eCRFs) presented in summary table will be presented in subject listings.

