#### ***8.4.4 Laboratory Data***

Actual values and change from baselines for all laboratory parameters will be summarized using descriptive statistics (serum chemistry, liver function tests, hematology, and serum erythropoietin) using SI units. Coagulation results will be listed only. Baseline is defined as the Screening measurement taken before the first dose of GBT440 for most labs. Baseline serum erythropoietin is Day 1.

A listing of all clinically significant laboratory values will be provided. Pregnancy results at each visit will be listed without summary. Listings will be presented with reported units and SI units.

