#### ***8.4.6 12-Lead Electrocardiogram***

HR (beats/min), PR interval (ms), QRS interval (ms), QT interval (ms), and QTc F interval (ms) will be summarized by the absolute value and change from baseline (Screening) at D90.

Additionally, the number and percentage of subjects with QTcF > 450 ms, >480 ms, and >500 ms at baseline and post-baseline measurement (Day 90 and Early Termination) will

be summarized by dose level and All GBT 440. The number and percentage of subjects with increase from baseline in QTcF of > 30ms and > 60 ms will also be summarized.

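### SAP 8.1 defines absolute change as baseline minus post-baseline, so the change summaries, if programmed as written, report rises as falls

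*SAP*

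**What the plan says.** SAP 8.1 gives one rule for absolute change, for all analyses in the plan: "Change from baseline to post-baseline values will be calculated by subtracting the post-baseline value from the baseline value". The next sentence begins "The percentage change from baseline values to post-baseline values will be calculated using the following formula", and the formula is the post-baseline value minus the baseline value, divided by the baseline value, times 100%.

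Three later sections rely on change from baseline without giving a formula of their own:

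- SAP 8.4.4, laboratory data: "Actual values and change from baselines for all laboratory parameters will be summarized using descriptive statistics". The section names serum chemistry, liver function, hematology and serum erythropoietin.
- SAP 8.4.5, vital signs, oximetry and physical examination: "Actual value and change from baseline for vital sign and pulse oximetry results including blood pressure", continuing to heart rate, respiratory rate, temperature, SpO2 and flow rate; and "Physical examination results including height, weight, and BMI will be summarized by the absolute value and change from baseline". Height is shown at Screening only.
- SAP 8.4.6, ECG: heart rate and the PR, QRS, QT and QTcF intervals "will be summarized by the absolute value and change from baseline (Screening) at D90". The same section adds a categorical summary: "The number and percentage of subjects with increase from baseline in QTcF of > 30ms and > 60 ms will also be summarized".

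These sections say which visits supply the baseline value, but not the direction of subtraction. The Protocol uses change from baseline throughout its endpoints and analysis sections and never defines its sign.

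**The concern.** Subtracting one quantity from another leaves the second minus the first, so the SAP 8.1 sentence defines change as baseline minus post-baseline. Under that rule a rise is negative and a fall is positive. This is the reverse of the percent-change formula beside it and of the direction a reader of a safety table would assume.

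The direction matters in this trial. Protocol 1.5.4 identifies tissue hypoxia as a theoretical risk of the drug and lists the signs to be watched: erythrocytosis, raised resting heart rate, erythropoietin, and laboratory evidence of organ injury such as liver aminotransferases. For each of these the signal is a rise, and followed as written the SAP would print it as a fall. The same reversal would show a gain in SpO2 as a loss and a lower oxygen flow rate as an increase.

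For laboratory values the usual companion summary is also absent. Protocol 11.3.2 says "Laboratory parameters will be summarized using descriptive statistics and by post-dose shifts relative to baseline", but SAP 8.4.4 plans no shift summary. Signed change is then the only planned tabulation of the direction of within-subject laboratory values themselves.

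**Working it through.** The plan gives no numerical result to reproduce here. The check is of the algebra and of how many outputs depend on it.

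**1. The two definitions.** Let B be the baseline value and P the post-baseline value.

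- Absolute change under SAP 8.1: B − P.
- Percent change under SAP 8.1: 100 × (P − B) / B.

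For any B > 0 and P ≠ B these have opposite signs. With illustrative values (assumed, not from the documents):

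| Variable | B | P | Absolute change as written (B − P) | Percent change as written | P − B |
|---|---|---|---|---|---|
| SpO2, % | 86 | 90 | −4 | +4.65% | +4 |
| O2 flow, L/min | 4 | 2 | +2 | −50% | −2 |
| QTcF, ms | 420 | 455 | −35 | +8.33% | +35 |
| Heart rate, bpm | 80 | 88 | −8 | +10% | +8 |

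**2. Effect on the planned statistics.** SAP 8.1 plans mean, SD, median, minimum and maximum. Reversing the sign of every observation gives:

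- printed mean = −(true mean)
- printed median = −(true median)
- printed minimum = −(true maximum)
- printed maximum = −(true minimum)
- printed SD = true SD

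Check with four made-up subjects, baselines 10, 12, 20, 30 and post-baseline values 15, 11, 28, 33. The differences P − B are +5, −1, +8, +3.

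| Rule | Mean | Median | Minimum | Maximum | SD |
|---|---|---|---|---|---|
| P − B | +3.75 | +4 | −1 | +8 | 3.77 |
| B − P (SAP 8.1) | −3.75 | −4 | −8 | +1 | 3.77 |

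The largest individual rise, 8, appears as a minimum of −8. The actual-value means, 18.00 at baseline and 21.75 afterwards, do show that values went up on average. The actual-value minima and maxima (10 and 30, then 11 and 33) do not show that the largest individual rise was 8, because they may come from different subjects.

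**3. Number of parameters affected.**

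- Hematology, Protocol 5.4.1.1: RBC, hematocrit, Hb, platelets, WBC, five differential counts and reticulocytes = 11; plus erythropoietin = 1.
- Chemistry, Protocol 5.4.1.2: 15.
- Liver function, Protocol 5.4.1.3: ALT, AST, ALK, GGT and three bilirubin measures = 7.
- Laboratory subtotal: 11 + 1 + 15 + 7 = 34.
- Vital signs and oximetry, SAP 8.4.5: systolic and diastolic pressure, heart rate, respiratory rate, temperature, SpO2, flow rate = 7.
- Weight and BMI, SAP 8.4.5 = 2.
- ECG, SAP 8.4.6: heart rate, PR, QRS, QT, QTcF = 5.
- Total: 34 + 7 + 2 + 5 = 48. Heart rate counts twice because it is summarized both as a vital sign and from the ECG.

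**4. The QTcF categories.** The 8.4.6 counts are worded as increases of more than 30 and more than 60 ms. Taken by that wording they are correct. If they are built from the 8.1 change variable, the assumed rise from 420 to 455 ms gives −35, which is not above 30, and the subject is missed; a fall of 35 ms would be counted instead.

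**The case against.** The best case for leaving this alone is that the intent is obvious. The percent-change formula and the QTcF wording both imply post-baseline minus baseline, so the sentence is almost certainly a transposed phrase. A competent programmer may never apply it literally. If it were applied, actual values are summarized beside the changes, and a reader could see that the mean change disagrees with the visit means. No information is destroyed: the largest rise is still in the table with its sign reversed, and SAP 8.1 puts the subject data behind summary tables into listings. The hypoxia signs in Protocol 1.5.4 are monitored in subjects during the study, which a summary column does not affect. The SAP serves an abbreviated safety report, is descriptive, and has no test or decision rule that uses signed change. No planned safety table prints percent change, so two contradictory columns would never appear together.

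These points are sound and limit the consequence to misreading of the report. One also narrows the laboratory point: clinically significant laboratory abnormalities are recorded as adverse events, or under the underlying diagnosis, and so reach the adverse event tables. Signed change is therefore not the only route by which a laboratory worsening could appear in a table, though it remains the only planned summary of within-subject change in the measured values.

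None of this makes the rule right. A programmer must either follow it and reverse the tables or depart from the approved plan without a documented reason, and anyone checking the output against the SAP would pass the reversed version.

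**Conclusion.** The concern holds. As written, SAP 8.1 reverses the sign of absolute change, contradicts its own percent-change definition, and is not corrected elsewhere in either document. If followed, it gives the wrong mean, median, minimum and maximum of change for 48 named parameters; the absolute sizes and the SDs are right.

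Not affected: actual-value summaries, the absolute QTcF thresholds (>450, >480, >500 ms), listings of reported values and the TEAE tables. The counts of QTcF increases are affected only if programmed from the 8.1 variable.

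The conclusion assumes only that the sentence is applied literally. It does not depend on the illustrative values. The error should be corrected before the tables are programmed. It does not threaten the trial's conduct or any inferential result.

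**What to change.** Replace the sentence in SAP 8.1 with: *Change from baseline = post-baseline value minus baseline value.* This agrees with the percent-change formula already there. In SAP 8.4.6 add a clause saying that the >30 ms and >60 ms QTcF increase categories use this variable.

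The cost is one sentence and one clause of SAP wording, made before programming. No new data are needed and no other analysis changes. If tables have already been programmed, check the direction of the change derivation against the corrected text.
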